# 3.3 Monitoring

Monitoring will be conducted in accordance with ICH-GCP E6 (5.18). Monitoring will be performed by the sponsor GWT-TUD GmbH.

# 3.4 Datamanagement

Datamanagement will be performed by the sponsor GWT-TUD GmbH.

# 3:3 Statistics

Statistic will be performed by the sponsor GWT-TUD GmbH. **3.3** 

# 3.6 Data and Safety Monitoring Board (DSMB)

A Bata Safety Monitoring Board (DSMB) of independent experts will be set up. It will consist of two physicians and one statistician who are not involved in the conduct of the trial. The task of the DSMB is to oversee the safety of the trial subjects in the clinical trial by periodically assessing

the safety and efficacy of the trial therapy and to monitor the integrity and validity of the data collected and the conduct of the clinical trial.

Throughout this process of surveillance, the DSMB will provide the sponsor with recommendations with regard to continuing the trial (e.g. termination or modification) based on the data collected. The data necessary for the DSMB to fulfill this function will be provided by the sponsor as determined by the DSMB charter.

# 3.7 Investigators and trial sites

The multicenter trial is planned to be conducted in up to 7 national trial sites in Germany by investigators with special expertise in the field of indication.

#### 3.7.1 Requirements for investigators and trial sites

The trial site will be required to have an investigator with at least 2 years experience in conducting clinical trials according to GCP as well as a substitute with comparable qualifications. The site must have a pool of suitable patients who can be recruited for the study.

All investigators must be qualified physicians. Each physician must supply his or her curriculum vitae (updated), a financial disclosure and certificates of GCP experiences for the TMF. All investigators must have skills in the assessment of endothelial function using prespecified techniques and should be familiar with anticoagulant treatment.

Investigators also must

- know main features of the law in Germany ("Arzneimittelgesetz") as well as legal and scientific basics of clinical trials
- know and sign the study protocol.

If any of the investigators are not physicians, these must be listed with reasons why they are suitable to be involved in the trial.

All investigators must sign the protocol signature sheet before subject recruitment and treatment may start. Likewise, all protocol amendments/integrated protocols must be signed and dated by the investigators before coming into effect.

# 3.8 Other study personnel

All other study personnel not included in this section are identified in a separate personnel list (not part of this clinical study protocol) as appropriate. This list will be updated as needed; an abbreviated version with personnel relevant for the center will be available in the center's investigator site file and the trial master file (TMF) of the sponsor.

# 3.9 Financing

The clinical trial will be financed by the sponsor GWT-TUD GmbH with a support of Bayer Vital GmbH. Bayer will also provide the IMP Rivaroxaban (Xarelto® 2.5 mg).

# 4 **Trial conduct**Time plan

First patient first visit (FPFV):	April 2015
Last patient first visit (LPFV):	July 2017
Last patient last visit (LPLV):	August 2018
Database Lock	December 2018
Final study report:	April 2019

#### 4.2 Design overview

This will be a multi center, open-label, controlled study with two treatment arms running in parallel. A total of 188 patients of both genders and older than 18 years with type 2 diabetes and documented high cardiovascular risk and low grade inflammation will be randomly assigned to one of two treatment groups:

Arm A:treatment group	Patients will receive Rivaroxaban 5 mg b.i.d. for the duration of 20 weeks.
Rivaroxaban	Additionally, 80 patients of the study population will continue to receive the Rivaroxaban 5 mg b.i.d. for a duration of 52 weeks (extension treatment).
Arm B: control group Aspirin	Patients will receive treatment with Aspirin 100 mg q.d. for the duration of 20 weeks. Additionally, 80 patients of the study population will continue to receive the Aspirin 100 mg q.d. for a duration of 52 weeks (extension treatment).

#### 4.2.1 Treatment groups

#### TABLE 1: TREATMENT GROUPS

7 study visits will be performed during the study. Subjects are obliged to come to the study center for 5 visits. Visits will take place at week -2 (screening - V0), day 0 (randomization/baseline - V1), at week 2 (V2), 4 (V3), 8 (V4), 12 (safety/compliance - V5) and week 20 (end of treatment for the first study period with vascular function test - V6).). Visit 3 and Visit 5 will be conducted as a telephone visit.

Additionally, 80 patients of the study population will perform 7 additional visits during the extension period. These visits will start after week 20. Patients attending the extension period will perform overall 14 study visits for 8 of these visits they will come to the study center whereas overall 6 visits are performed as telephone visits. The additional visits will take place at week 24

(V7), week 28 (V8), week 32 (V9), week 36 (V10), week 40 (V11), week 44 (V12) and week 52 (end of treatment extension - V13). Visit 7, 9, 11 and 12 will be conducted as a telephone visit. Measurements of FBF, LDF and pletysmography at baseline-visit, visit week 20 (V6) and EOT-visit (V13) can be done up to 3 days after the visits in the corresponding study location that provides these measurements. Patients will be informed of the procedure by the physician.

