# Pulse wave velocity and arterial stiffness:

	Measurements will be performed using the Mobil-O-Graph device (IEM Inc., Stolberg, Germany). This device allows the non-invasive oscillometric analysis of blood pressure and pulse wave over 24 hours. Based on pulse wave analysis we calculate the aortic augmentation index as marker of arterial stiffness and pulse wave velocity. The Mobil-O-Graph device has been validated against gold standard procedures such as applanation tonometry (SphygmoCor, AtCor Inc.).	
Measurement of	Assessment of platelet activation and mitogenic potential	
results	Platelet activation will be assessed by measuring platelet derived microparticles (PMP) by separating platelet poor plasma from platelet rich plasma. Subsequently, analysis of platelet microparticles and their mitogenic potential will be performed after sample thawing. PMP will be measured after staining with anti-GP1b antibodies by fluorescence-activated cell sorting (FACS). In addition, magnetic beads linked with anti-GP1 b antibodies will be used to extract PMP from platelet poor plasma. Extracted PMP will then be added to human vascular endothelial cells (HUVECS) and migration (Boyden chamber) as well as proliferation (BrdU) of HUVECs will be assessed with and without PMP with samples from patients undergoing platelet inhibition or rivaroxaban treatment. Platelet rich plasma will be used to measure platelet activation by cGMP dependent phosphorylation of vasodilator-stimulated phosphoprotein (VASP) at Ser-157 which will be detected by flow cytometry.	
Statistical methods	Efficacy: The statistical analysis will be done in the intention to treat and per protocol set. The primary parameter will be the maximum FBF at 20 weeks (assessed with venous occlusion plethysmography after forearm ischemia) controlling for baseline FBF and the Pulse Wave Velocity (PWV) at EOT (extended treatment period after 52 weeks) assessed with a sphygmograph (Mobilograph®, IEM) using an analysis of covariance (ANCOVA). Independent t-test will be used to test the parameters between the groups at the time point as well as the change between baseline and 20 weeks of treatment. Additionally, measurements will also be compared to an extended treatment up to 52 weeks (EOT Extension). Safety: Analysis of bleeding events and safety parameters is required.	

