# 2 **Objectives of the clinical trial**

Objectives of this clinical trial are the in vivo assessment of microvascular function using different non-invasive techniques and the in vitro assessment of biomarkers of endothelial damage, inflammation and coagulation/fibrinolysis before and after treatment with either aspirin or rivaroxaban in type 2 diabetic patients with high cardiovascular risk and inflammation. Furthermore possible functional interactions between mononuclear blood cells and platelets as well as expression of mRNA (and protein) within these cells before and after treatment in vitro will be assessed.

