#### 4.13.2 Visit 1 –Baseline (day $0 \pm 4 d$ )

The following actions/measures will be performed:

- check adherence to inclusion / exclusion criteria
- questioning for adverse events, suspected or verified pregnancy and concomitant medication

- measurement blood pressure, heart rate (after resting for at least 3 min in supine position)
- measurement of forearm blood flow
- laserdopplerfluxometry (LDF)
- measurement of arterial stiffness
- efficacy laboratory parameter for endothelial function and coagulation
- efficacy laboratory for composite of biomarkers of inflammation
- blood samples for assessment of platelet function / mitogenic potential
- safety laboratory parameter
- assessment of metabolic marker and cardiovascular marker
- dispensing of study drug along with intake prescriptions

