# 5.8 Assignment of trial subjects to treatment groups

All eligible patients will be randomized at baseline visit V1 (after necessary laboratory parameters are available) using a central block randomization process based at the sponsor's site. The study site requesting randomization of a patient will send a form containing site ID and screening number to the sponsor (Dept. of Medical Consulting; [contact]**, in the time frame Monday to Friday 8.00 am to 4.00 pm, not on legal holidays). In return, the site will receive a randomization form containing the randomization number and allocation to treatment arm by fax or email within 30 min.

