## 5.9 Selection of dosage of IMP and frequency of treatment

Rivaroxaban will be administered at a dose of 5 mg ( $2 \times 2.5$  mg) twice daily (each 12 h), aspirin will be administered at a dose of 100 mg once daily (each 24 h).

The first dose of either study drug will be administered to the participants at the day of randomisation (visit 1). Further administrations take place at Visit 2 (after 2 weeks) and visit 4 (after 8 weeks).

Rivaroxaban will be administered according to the described instructions. Dosage and frequency of aspirin treatment applied in this study will follow the general specifications of the given SmPC. For patients participating in the extended treatment period, drug dispense will additionally take place at visit V6 (after 20 weeks), at visit V8 after 28 weeks and at visit V10 after 36 weeks.

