#### 4.8 Definition of derived variables

#### 4.8.1 Primary variable

#### ΔFBF:

 $\Delta$ FBF (ml/100ml) will be composed of 5 IR baseline measurements and 8 measurements of post-ischemic blood flow. Repeated measurements for IR baseline per visit will be summarized by arithmetic mean.

Changes in FBF (ml/100ml) will be calculated as IR post-ischemic – IR baseline (mean).

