#### 6.3 Hypothesis Testing

Unless otherwise specified all hypotheses will be tested at a 5% level of significance against two-sided alternative hypotheses.

Continuous variables will be analyzed by the following test procedures:

First of all the assumption of normally distributed data will be checked with Shapiro-Wilk test by treatment group. If the hypothesis of normally distributed data cannot be rejected for both treatment groups treatments will be compared by an ANCOVA procedure which includes "treatment" as the main factor and "baseline value" as covariate. T-Tests for independent samples will be used to compare groups at baseline.

In the event that the normality assumption is not warranted, data will be log-transformed and normality assumption of the transformed data will be checked by Shapiro-Wilk test. In case of non-rejection of the hypothesis of normally distributed data for both treatment groups, ANCOVA procedure and t-tests as described above will be performed on the basis of log-transformed data.

Point estimates and 95% CI of the difference in (adjusted) mean change from baseline will be provided if data are evaluated on basis of an ANCOVA procedure.

Otherwise Mann-Whitney's-U test on the basis of original data will be applied for comparison of groups at baseline. Mann-Whitney's-U test on the basis of intra-individual differences to baseline will be applied for treatment comparison per visits after baseline. Wilcoxon's signed rank test will be applied to evaluate changes from baseline per treatment group.

Categorical variables with 2 categories will be analyzed using Fisher's exact test (with Yates correction) to compare proportions between treatment groups. Variables with more than 2 categories will be compared by Pearson's Chi-square test. Additionally for each category, the proportions of treatment groups are compared using an (asymptotic) z test. Significant differences in proportions will be flagged, p-values for the z-test will not be shown.

Missing values will not be imputed.

If necessary, modifications of this general procedure will be described in the following sections of chapter 6.

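### Baseline FBF and LDF may be measured up to 3 days after V1, where study drug starts, so a compliant day-0 value can be post-dose, and no analysis rule identifies it

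*Protocol*

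**What the plan says.** **Measurement timing.** Protocol 4.2.1 covers FBF, LDF and plethysmography at the baseline visit, V6 and V13, and states that they "can be done up to 3 days after the visits in the corresponding study location that provides these measurements".

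**Start of treatment.** The V1 procedures in Protocol 4.13.2 end with "dispensing of study drug along with intake prescriptions". Protocol 5.9 adds: "The first dose of either study drug will be administered to the participants at the day of randomisation (visit 1"; it sets a 12-hour interval for rivaroxaban and a 24-hour interval for aspirin. Neither section makes the first dose wait for a delayed measurement.

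**Aim.** Protocol 2 describes assessment "before and after treatment with either aspirin or rivaroxaban"; SAP 2.3 repeats it.

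**Use of the day-0 value.**
- SAP 4.8.1 defines ΔFBF within a session: "Changes in FBF (ml/100ml) will be calculated as IR post-ischemic" minus the mean of the resting values.
- SAP 6.11.1 sends the primary comparison to the procedures for continuous data. In SAP 6.3 these are an ANCOVA with treatment "as the main factor and 'baseline value' as covariate". The Protocol synopsis likewise has the primary parameter analysed "controlling for baseline FBF".
- Protocol 6.1.1 and 9.2 define the primary variable as a change and test it with an independent-samples t-test.
- The mock tables in SAP 7.6.1 compare arms on changes in ΔFBF from day 0.

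**The concern.** A baseline supports adjustment or a change score only if treatment cannot have altered it. Here a site that follows the Protocol exactly can deliver a day-0 FBF taken after up to three days of randomised treatment. In an open-label trial, that value is also obtained with the allocation known.

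If the arms already differ by then, part of the treatment effect enters the covariate or the subtracted baseline and is removed from the primary contrast. Without a rule based on measurement and intake times, the report cannot show that the baseline for its primary endpoint was pre-treatment.

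**Working it through.** **1. Can a compliant value be post-dose?** The allowance is 3 days = 72 h after V1, and the first dose is on the day of V1. Doses possible by then: rivaroxaban 72/12 = 6; aspirin 72/24 = 3. So yes.

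**2. Does another rule catch it?**
- Protocol 4.12.1 records time deviations as protocol deviations, but a measurement inside the 3-day allowance is permitted.
- SAP 4.5 names only the nominal times: day 0, week 20 and week 52.
- SAP 3.3 requires complete V1 and V6/V13 data for the PPS, with no pre-dose condition. Its data review meeting and the deviation listing in SAP 6.4 carry no timing criterion.
- SAP 4.6 has a baseline substitution rule for metabolic markers. FBF has none.

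**3. The plan's own sample size.** Difference 1.2, SD 2.4 ml/100ml, one-sided α 0.05, power 0.90 (Protocol 9.1.8). The t-test needs 69.2, so 70 per arm; 70/0.75 = 93.3, rounded up to 94 per arm, 188 in total; 188 × 0.75 = 141 evaluable. The plan's figures reproduce. With 70 and 71 evaluable per arm, power is 0.905.

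**4. How contamination would act.** Let s be the share of baselines taken late, e the between-arm effect on FBF already present in those patients, and b the weight given to the day-0 value. The shift in the contrast is b × s × e. For a change score b = 1; for ANCOVA b is the regression slope on baseline. The documents give none of s, e or b, so the values below are assumptions.

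| Change-score t-test (b = 1) | Shift, ml/100ml | Expected difference | Power |
|---|---|---|---|
| No late baselines | 0 | 1.2 | 0.905 |
| s = 0.10, e = 0.12 | 0.10 × 0.12 = 0.012 | 1.188 | 0.900 |
| s = 0.25, e = 0.6 | 0.25 × 0.6 = 0.15 | 1.05 | 0.826 |

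Power drops below 0.80 only if the loss exceeds 15.8% of the effect: 0.158 × 1.2 = 0.19 ml/100ml.

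Under ANCOVA with s = 0.25 and e = 0.6, slopes of 0.3, 0.5 and 0.8 give shifts of 0.045, 0.075 and 0.12 ml/100ml. I attach no power to these. A useful covariate also reduces the residual SD below that of the unadjusted comparison, so keeping 2.4 would overstate the loss.

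**5. Week 20 (secondary).** Drug is returned at V6 and dispensed again only to patients entering the extension (Protocol 4.13.5). A week-20 FBF taken in the days after V6 may therefore be on-drug in some patients and off-drug in others. Protocol 5.11.1 gives rivaroxaban a half-life of 7 to 11 h and calls aspirin's platelet inhibition irreversible, so a gap need not act equally in both arms. Week-52 PWV is not clearly affected, because the allowance does not name arterial stiffness.

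**The case against.** **The effect may be trivial.** Protocol 1 describes FBF changes as occurring within a few weeks, so half of the 20-week effect within three days, as in the 0.826 case, is a strong assumption. The milder case loses almost nothing. If rivaroxaban raises FBF early, the shift is towards no effect, which is conservative for a one-sided superiority test. All of this stands, and it limits how much weight the illustration can carry.

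**Late baselines may be uncommon.** At most 7 sites are planned (3.7), and investigators must have skills in the prespecified techniques (3.7.1). The V1 list in 4.13.2 also places FBF and LDF before dispensing, which suggests that pre-dose measurement was intended. But list order is not a rule and does not cover a measurement made days later elsewhere. Site manuals or intake instructions outside these documents may add a restriction; the Protocol and SAP state none.

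**The covariate role is partly inferred.** SAP 6.11.1 specifies a repeated-measures ANCOVA with AR(1) structure, ranks as fallback, and optional age, gender and diabetes duration. It does not itself list the baseline value. That enters through the general procedure in 6.3, and the Protocol synopsis states it directly.

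**Stronger readings that a reader might infer.**
- *A definite loss of power in the SAP's ANCOVA.* Not supported: slope, residual SD, late share and early effect are all missing.
- *More than half of evaluable patients off drug at week 20.* That would require applying dropout before V6 to extension patients, who must reach V6 to enter the extension.
- *A contradiction between the 3-day allowance and the ±2-day window at V6.* The first counts from the visit and the second places the visit, so both can operate together.

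**Conclusion.** The point holds as a defect in the plan's rules. The Protocol permits a post-dose baseline for the primary endpoint and for LDF, against its own before-and-after aim, and no analysis rule separates such values. This rests on reading Protocol 4.2.1, 4.13.2 and 5.9 together and needs no assumption about frequency.

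The consequence is not quantifiable from the documents. Size and direction of bias are unknown, and it may be negligible. The drop in power from 0.905 to 0.826 belongs to the change-score t-test alone, under an assumed 25% late share and 0.6 ml/100ml early effect. A reader might infer that the primary result must be biased, or biased in favour of rivaroxaban; the documents show neither. The possible mix of on-drug and off-drug values at week 20 is secondary, because the plan does not say which is intended. The point is worth fixing because it touches the primary baseline and the remedy is cheap.

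**What to change.** 1. Reconcile Protocol 4.2.1 with sections 2, 4.13.2 and 5.9 and with SAP 2.3, leaving dosing unchanged, so that the baseline FBF/LDF window ends before first intake (for example, booked in the days up to V1).
2. State first whether week-20 and week-52 FBF/LDF values are meant to be on-drug; then set those windows to match.
3. Record date and time of each measurement and of first and last intake. The medication diary (Protocol 5.7) and source records (7.1.2) can help to supply them.
4. Prespecify in the SAP, before database lock, two sensitivity analyses for the primary endpoint: (a) excluding baselines taken after first intake, with counts by arm; (b) comparing week-20 ΔFBF without the day-0 covariate. A post-dose baseline cannot bias (b), and it excludes nobody for baseline timing. If measurements are already complete, both remain possible before lock, with (a) relying on source dates.

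Cost: earlier booking at sites without the equipment, a few date and time fields, short additions to both documents, and lower precision in the sensitivity analyses.

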#### 4.2.2 Visit schedule

#### 4.2.2.1 Visit schedule for 20 Weeks of treatment

Visit	V0	V1	V2	V3	V4	V5	V6
specification	screening	baseline		telephone		telephone	
week	day -28	day 0	2	4	8	12	20
timeframe		+/- 4 d	+/- 2 d	+/- 2 d	+/- 2 d	+/- 2 d	+/- 2 d

#### 4.2.2.2 Additional visits for extension period (52 weeks of treatment)

Visit	V7	V8	V9	V10	V11	V12	V13
specification	telephone		telephone		telephone	telephone	EOT
week	24	28	32	36	40	44	52
timeframe	+/- 2 d	+/- 2 d	+/- 2 d	+/- 2 d	+/- 2 d	+/- 2 d	+/- 2 d

#### TABLE 2: VISIT SCHEDULE (TV - TELEPHONE VISIT)

#### 4.3 End of the clinical trial

After conclusion of the clinical trial, patient will receive standard medical care as usual for this kind of disease. Interim analyses are not planned.

As for this study the primary objective will be analyzed after LPLV, the end of the study as a whole will be the date when the clean database is available.

#### 4.4 Justification of trial design

For study objectives, see section 2. For selection of doses, see section 5.9.

# 4.5 Selection of trial population

Male and female subjects older than 18 years and suffering from type 2 diabetes and CVD are to be screened for participation in the present study according to the inclusion and exclusion criteria described in section 4.11.

An individual subject may only be included once in the study.

# 4.6 Justification of gender distribution

Male and female subjects will be included in the present study representing the population of patients suffering from type 2 diabetes and CVD without any gender prevalence.

# 4.7 Justification of selection criteria

The selection criteria are chosen to ensure that subjects with specific risks for administration of the study medication and / or subjects with conditions which may have an impact on the aims of the study are excluded.

